10.1.5. Prior and Concomitant Therapy

Concomitant medications will be coded using the World Health Organization Drug Dictionary drug codes. Concomitant medications will be further coded to the appropriate Anatomical Therapeutic Chemical code indicating therapeutic classification. Prior and concomitant medications will be summarized by dose level.

Prior medications will be defined as medications that started before the dose of study drug. Concomitant medications will be defined as medications that (1) started before the dose of study drug and were continuing at the time of the dose of study drug, or (2) started on or after the date of the dose of study drug up to 30 days after the dose of study drug.

10.2. Efficacy Analyses

There is no efficacy analysis planned for this study.

10.3. Safety Analyses

Adverse events, ECGs, vital signs, and laboratory data will be reviewed and summarized on an ongoing basis during the study to evaluate the safety of subjects. Descriptive statistics will be used to analyze all safety data.

10.3.1. Extent of Exposure

The extent of study drug exposure will be summarized descriptively for the single dose administered by dose level. The number (percentage) of subjects with dose interruption and infusion rate decreased will be summarized with the respective reasons by dose level.

Subject data listings will be provided for all dosing records and for calculated summary statistics.

10.3.2. Adverse Events

The AE verbatim descriptions (as recorded by the investigator on the eCRF) will be classified into standardized medical terminology using the Medical Dictionary for Regulatory Activities (MedDRA). Adverse events will be coded to MedDRA by the lowest level term, preferred term (PT), and primary system organ class (SOC).

A TEAE is defined as an AE that had an onset date or a worsening in severity from baseline on or after the administration of study drug and up to 30 days after the dose of study drug. Only those AEs that were treatment-emergent will be included in summary tables.

The incidence of TEAEs will be reported as the number (percentage) of subjects with TEAEs by SOC and PT. A subject will be counted only once by the highest severity grade according to NCI-CTCAE version 5.0 within a SOC and PT, even if the subject experienced more than one TEAE within a specific SOC and PT.

The number (percentage) of subjects with TEAEs will also be summarized by relationship to the study drug. Treatment-related AEs include those events considered by the investigator to be related to study drug or with missing assessment of the causal relationship. Treatment-emergent SAEs and treatment-related TEAEs will also be summarized. All AEs, treatment-emergent or otherwise, will be presented in subject data listings.

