9.3.5. Laboratory Test Abnormalities

Abnormal laboratory findings (eg, clinical chemistry, complete blood count, coagulation, or urinalysis) or other abnormal assessments (eg, ECGs, cardiac telemetry, or vital signs) that are judged by the investigator as clinically significant will be recorded as AEs or SAEs. This includes clinically significant abnormal laboratory findings or other abnormal assessments that are present at baseline and significantly worsen during the study. The definition of clinically significant is left to the judgment of the investigator. In general, these are laboratory test abnormalities or other abnormal assessments that:

- are associated with clinical signs or symptoms, or
- require active medical intervention, or
- lead to dose interruption or discontinuation, or
- require close observation, more frequent follow-up assessments, or
- further diagnostic investigation.

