9.6. Timing, Frequency, and Method of Capturing Adverse Events and Serious Adverse Events

9.6.1. Adverse Event Reporting Period

After informed consent has been signed but prior to the administration of the study drug, only SAEs should be reported.

After initiation of the study drug, all AEs and SAEs, regardless of relationship to study drug, will be reported until 30 days after the dose of study drug or EOS Visit, whichever is later. After the period, the investigator should report any SAEs that are considered to be related to the study drug.

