4. STUDY ENDPOINTS

4.1. Primary Endpoint

 Incidence and severity of treatment-emergent adverse events (TEAEs) and treatment-emergent serious adverse events (SAEs)

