6.3.4. Prior and Concomitant Medications

Prior medications will be defined as medications that started and stopped before the dose of study drug. Concomitant medications will be defined as medications that (1) started before the dose of study drug and were continuing at the time of the dose of study drug, or (2) started on or after the date of the dose of study drug up to 30 days after the dose of study drug.

Prior and concomitant medications will be coded using the version of World Health Organization Drug Dictionary (WHO DD) drug codes currently in effect at BeiGene at the time of database lock. They will be further coded to the appropriate Anatomical Therapeutic Chemical (ATC) code indicating therapeutic classification.

The number (percentage) of subjects reporting prior and concomitant medications will be summarized by ATC medication class and WHO DD preferred name in the Safety Analysis Set. A listing of prior and concomitant medications will be provided.

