6.5.2. Adverse Events

The AE verbatim descriptions (investigator terms from the eCRF) will be classified into standardized medical terminology using MedDRA. Adverse events will be coded to the MedDRA lowest level term closest to the verbatim term, along with the linked MedDRA PT and primary SOC.

A TEAE is defined as an AE that had an onset date or a worsening in severity from baseline on or after the administration of study drug and up to 30 days after the dose of study drug. Summary tables will generally focus on those AEs that were treatment-emergent. All AEs, treatment-emergent or otherwise, will be presented in subject data listings.

If any of the following TEAEs occurs, the administration of the study drug and the enrollment of new subjects will pause for the dose level:

- One or more ≥ Grade 4 TEAEs or treatment-emergent SAEs related to study drug as assessed by the investigator in any subject or
- Grade 3 TEAEs related to study drug as assessed by the investigator in 2 or more subjects at the same dose level.

An AE overview table, including the number of subjects with TEAEs, TEAEs with grade 3, TEAEs with grade 4 or higher, treatment-emergent SAEs, TEAEs that led to death, TEAEs that led to treatment discontinuation, TEAEs that led to treatment modification for study drug, and treatment-related TEAEs, will be provided by dose level. Treatment-related AEs include those events considered by the investigator to be related to study drug or with a missing assessment of the causal relationship.

The incidence of TEAEs will be reported as the number (percentage) of subjects with TEAEs by SOC, PT and the worst grade. A subject will be counted only once by the highest severity grade according to NCI-CTCAE version 5.0 within a SOC and PT, even if the subject experienced more than one TEAE within a specific SOC and PT. The number (percentage) of subjects with treatment-emergent SAEs will be summarized by SOC and PT.

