6.5.3. Laboratory Values

Clinical laboratory values will be evaluated for each laboratory parameter as appropriate.

Descriptive summary statistics (n, mean, standard deviation, median, Q1, Q3, minimum, and maximum for continuous variables; n [%] for categorical variables) for laboratory parameters and their changes from baseline will be summarized by visit and dose level. Change from baseline will only be summarized for subjects with both baseline and postbaseline measurements.

Laboratory parameters that are graded in NCI-CTCAE v5.0 will be summarized by shifts from baseline CTCAE grades to maximum postbaseline grades. In the summary of laboratory parameters by CTCAE grade, parameters with CTCAE grading in both high and low directions will be summarized separately.

Subject data listings of each parameter will be provided. Abnormal values will be flagged and identified as those outside (above or below) the normal range.

BeiGene 12 May 2021

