8. CHANGES IN THE PLANNED ANALYSIS

Not applicable.

BeiGene 12 May 2021

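### AEs and SAEs that start more than 30 days after the dose are collected to Day 113 but appear in no planned AE table

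*Protocol*

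**What the plan says.** **Collection.** Under Protocol 9.6.1, all AEs and SAEs after dosing, regardless of relationship, "will be reported until 30 days after the dose of study drug or EOS Visit, whichever is later". Protocol 7.6.2 makes Day 113 the EOS Visit for subjects who complete the schedule.

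**Tabulation.** Protocol 10.3.2 closes the TEAE window at 30 days and excludes everything else from the tables: "up to 30 days after the dose of study drug. Only those AEs that were treatment-emergent will be included in summary tables". SAP 6.5.2 repeats the window with looser wording on tables: "Summary tables will generally focus on those AEs that were treatment-emergent". The tables it then names are an overview, TEAEs by system organ class (SOC), preferred term (PT) and worst grade, and SAEs by SOC and PT. All are restricted to treatment-emergent events. Both documents send the remaining AEs to listings. The primary endpoint (Protocol 2.2.1, SAP 4.1) is worded in terms of TEAEs and treatment-emergent SAEs.

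**Related rules.** Laboratory parameters with CTCAE grades are "summarized by shifts from baseline CTCAE grades to maximum postbaseline grades" (SAP 6.5.3), with no 30-day limit. Protocol 9.3.5 says that abnormal laboratory findings "that are judged by the investigator as clinically significant will be recorded as AEs or SAEs". SAP 6.3.4 counts a new drug as concomitant only if it "started on or after the date of the dose of study drug up to 30 days after the dose of study drug", and Protocol 10.1.5 has the same limit. SAP Section 8 declares no change from the protocol's planned analysis.

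**The concern.** The primary objective is the safety and tolerability of a single dose, stated without a time limit, for an antibody expected to persist for weeks. Subjects are followed to Day 113, yet the planned AE tables describe only the first 30 days. A late clinical event, including one that follows ADA development, would have no planned incidence by dose level and no tabulated comparison with the pooled placebo arm. The analysis that might cover this period, the effect of immunogenicity on safety, is optional and deferred to a separate plan (SAP 6.7).

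The SAP also treats late data unevenly. A clinically significant abnormality in a CTCAE-graded laboratory parameter, first seen on Day 57, is recorded as an AE and counted in the laboratory shift table, but enters no AE table. A drug started on Day 40 is recorded in the eCRF (Protocol 6.2) but is neither prior nor concomitant under SAP 6.3.4.

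**Working it through.** **1. Calendar check.** There is no Day 0, so Day 113 is (113 − 1) × 24 = 2688 hours after dosing. This matches the time printed in Protocol Appendix 3. Post-dose follow-up for a completer is therefore 112 days.

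**2. Time outside the window.** Thirty days after the dose is study Day 31.
- Untabulated time: 112 − 30 = 82 days; 82/112 = 73%.
- Scheduled visits after Day 1 (Appendix 1): Days 2, 3, 4, 5, 8, 15, 22, 29, 43, 57, 71, 85 and 113, which is 13. The last five fall after the window: 5/13 = 38%.
- Post-baseline ADA samples (Appendix 3): Days 15, 29, 57, 85 and 113. The last three fall after the window: 3/5.
- Haematology, chemistry, coagulation and urinalysis are scheduled on Days 57, 85 and 113, so late laboratory AEs can be detected.

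**3. Drug exposure after the window (context only).** Inputs are the human projections in Protocol Table 1: CL 0.0075 L/h, Vc 2.96 L, Q 0.033 L/h, Vp 2.41 L. The 30–60 minute infusion is treated as a bolus.
- k10 = CL/Vc = 0.00253, k12 = Q/Vc = 0.01115 and k21 = Q/Vp = 0.01369 per hour.
- β = [s − √(s² − 4·k10·k21)]/2 with s = k10 + k12 + k21, giving β = 0.001332 per hour; α = s − β = 0.02604 per hour.
- Terminal half-life = ln 2/β ÷ 24 = 21.7 days; 30/21.7 = 1.4 half-lives.
- With A = (α − k21)/(α − β) = 0.500 and B = (k21 − β)/(α − β) = 0.500, the share of AUCinf after 720 h is [(A/α)e^(−720α) + (B/β)e^(−720β)] / (A/α + B/β) = 36%.

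Table 1 gives no human variability. As an assumption, CL is varied by the monkey inter-individual figure of 26.9%:

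| CL multiplier | Half-life (days) | Half-lives in 30 days | AUCinf after 30 days |
|---|---|---|---|
| 0.731 | 29.3 | 1.0 | 47% |
| 1 | 21.7 | 1.4 | 36% |
| 1.269 | 17.3 | 1.7 | 28% |

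**4. Effect on a reported rate.** With 6 active subjects per level, each subject whose only AE is late makes the 30-day incidence 1/6 = 16.7 percentage points lower than the dose-to-EOS incidence. The TEAE incidence itself is unchanged; the figure is the difference between two summaries.

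**5. Placebo comparator.** Two placebo subjects per level give 2 × 2 = 4 for the two planned levels, or 2 × 3 = 6 if Level C opens.

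**The case against.** The plan is internally consistent. The primary endpoint is defined on TEAEs, and the same 30-day definition appears in the synopsis, Protocol 10.3.2 and SAP 6.5.2. Late events are not lost: they are listed by subject, SAEs are reported within 24 hours, and AEs are reviewed and summarized on an ongoing basis (Protocol 10.3). Laboratory, vital-sign and ECG by-visit summaries run to EOS. With at most 30 subjects and no inferential statistics, a reader could count late events from a listing, and a placebo arm of 4 to 6 adds little. The SAP's looser wording leaves room for an extra table. The likeliest risk the protocol names, infusion reactions, is early, and 8 of the 13 post-Day-1 visits fall inside the window. The share of AUC after Day 30 measures exposure, not event risk.

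Much of this stands. There is no contradiction, the exposure figures are only context, no late-event rate is known, and the placebo arm is small. But permission to make a table is not a commitment to make one. Listings give no incidence by dose level or against placebo, which is how this SAP reports its other AEs. The laboratory, vital-sign and ECG summaries do not capture clinical AEs.

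**Conclusion.** The concern holds. For completers, 82 of 112 post-dose days are under full AE collection but outside every AE table the SAP names. This rests on the documents' text and calendar arithmetic. For subjects who leave early, collection ends at the later of 30 days or their own EOS Visit, so their gap is shorter or absent. The half-life and AUC figures depend on Table 1 projections and an assumed range for CL, and the conclusion does not need them. The planned 30-day tables are valid for the endpoint as defined; on their own they leave most of the safety follow-up without a summary. The change should be made, but the primary endpoint does not have to be redefined.

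**What to change.** - **SAP 6.5.2:** commit to AE and SAE incidence tables from dosing through EOS: overall, by SOC, PT and worst grade, and treatment-related, by dose level and for pooled placebo. Present them beside the 30-day TEAE tables, which stay as they are.
- **SAP 6.3.4:** extend the concomitant-medication window to EOS.
- **SAP Section 8:** record both changes, because Protocol 10.3.2 limits summary tables to TEAEs and Protocol 10.1.5 has the same 30-day medication window. Sponsor biostatistics is unblinded (Protocol 5.3), so date the entry and give the reason, to show that the addition was not prompted by the data.

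If the sponsor prefers to lengthen the TEAE definition itself, the pausing criteria in Protocol 3.3 and SAP 6.5.2 use that term, and their wording would have to be reconciled with the new definition.

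The cost is SAP text and one further set of tables; no new data or visits are needed. The drawback is more background events in the longer tables. Placebo subjects have the same follow-up and help with interpretation, though there are only about 4 to 6 of them under the planned cohorts.

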10.3.3. Laboratory Analyses

Clinical laboratory (clinical chemistry, hematology, coagulation, and urinalysis) values will be evaluated for each laboratory parameter as appropriate. Abnormal laboratory values will be flagged and identified as those outside (above or below) the normal range. Laboratory parameters and their changes from baseline will be summarized by visit and dose level. Change from baseline will only be summarized for subjects with both baseline and postbaseline measurements.

10.3.4. Vital Signs

Descriptive statistics for vital sign parameters (systolic and diastolic blood pressure, pulse rate, respiratory rate, and body temperature) and changes from baseline will be summarized by visit and dose level.

10.3.5. Electrocardiogram

Descriptive statistics for ECG parameters and changes from baseline will be summarized by visit and dose level.

10.4. Pharmacokinetic Analyses

Noncompartmental analysis will be carried out for BGB-DXP593 serum concentrations. The PK analyses will include only subjects with enough data to enable estimation of key parameters.

Parameters, such as C_{max} , t_{max} , $t_{1/2}$, AUC_t , AUC_{inf} , AUC_{0-29} , CL, and V_z (as appropriate for data collected), may be derived and summarized with descriptive statistics (sample size, mean, standard deviation, coefficient of variance, median, minimum, maximum, geometric mean, geometric coefficient of variance). Other PK parameters may be calculated if supported by the data. Individual serum concentration-versus-time data will be tabulated and plotted by dose level. Additional PK analyses (such as modeling and simulation using nonlinear mixed effects modelling) may be conducted as appropriate.

10.5. Immunogenicity Analyses

The immunogenicity results will be summarized using descriptive statistics by the number and percentage of subjects who develop detectable ADAs. The incidence of positive and neutralizing ADAs will be reported for evaluable subjects. The effect of immunogenicity on PK, and safety may be evaluated if data allow.

10.6. Sample Size Consideration

A sample size of 8 subjects at each dose level (6 active and 2 control) totaling up to 30 subjects (including possible replacement) is not based on any statistical considerations. The sample size is based on the clinical consideration to provide safety and tolerability information and pharmacological considerations with the need to minimize exposure to healthy subjects at each dose level. No formal inferential statistics will be applied to the safety or PK data.

10.7. Interim Analysis

There is no formal interim analysis planned for this study.

11. STUDY COMMITTEE

11.1. Safety Monitoring Committee

An SMC will be established and will include both the sponsor (including the medical monitor and study team members from Pharmacovigilance/Drug Safety, Clinical Pharmacology, and Biostatistics with other members as appropriate) and investigators.

The SMC will review safety, laboratory data and make recommendations on dose escalations for this study. The SMC may also be called upon by the sponsor on an ad hoc basis where applicable to the conduct of the study.

A separate charter will outline the details for the composition and responsibility of the SMC.

12. SOURCE DOCUMENTS AND ACCESS TO SOURCE DATA/DOCUMENTS

The investigator must maintain adequate and accurate records to ensure that the conduct of the study may be fully documented. Such records include but are not limited to the protocol, protocol amendments, ICFs, and documentation of IRB/IEC and governmental approvals. In addition, at the end of the study, the investigator will receive subject data, which will include an audit trail containing a complete record of all changes to such data.

12.1. Access to Information for Monitoring

In accordance with International Council for Harmonisation GCP guidelines, the study monitor must have direct access to the investigator's source documentation to verify the data recorded in the eCRFs for consistency.

The monitor is responsible for routine review of the eCRFs at regular intervals throughout the study to verify adherence to the protocol and the completeness, consistency, and accuracy of the data being entered on them. The monitor should have access to any subject records needed to verify the entries in the eCRFs. The investigator agrees to cooperate with the monitor to ensure that any problems detected during these monitoring visits are resolved.

12.2. Access to Information for Auditing or Inspections

Representatives of regulatory authorities or of BeiGene may conduct inspections or audits any time during or after completion of this clinical study. If the investigator is notified of an inspection by a regulatory authority, the investigator agrees to notify the sponsor or its designee immediately. The investigator agrees to provide to representatives of a regulatory agency or BeiGene access to records, facilities, and personnel for the effective conduct of any inspection or audit.

13. QUALITY ASSURANCE AND QUALITY CONTROL

13.1. Regulatory Authority Approval

The sponsor will obtain approval to conduct the study from the appropriate regulatory agency in accordance with any applicable country-specific regulatory requirements or file the protocol to the appropriate regulatory agency before the study is initiated at a study center in that country.

13.2. Quality Assurance

To ensure compliance with GCP and all applicable regulatory requirements, the sponsor may conduct a quality assurance audit. Regulatory agencies may also conduct a regulatory inspection of this study. Such audits/inspections can occur at any time during or after completion of the study. If an audit or inspection occurs, the investigator and institution agree to allow the auditor/inspector direct access to all relevant documents and to allocate his/her time and the time of his/her personnel to the auditor/inspector to discuss findings and any relevant issues.

13.3. Study Site Inspections

This study will be organized, performed, and reported in compliance with the protocol, standard operating procedures, working practice documents, and applicable regulations and guidelines. Site audits may be performed periodically by the sponsor's or the contract research organization's qualified compliance auditing team, which is an independent function from the study team responsible for conduct of the study.

Site visits will be conducted by the sponsor or an authorized representative to inspect study data, subjects' medical records, and eCRFs. The investigator is to permit national and local health authorities; sponsor study monitors, representatives, and collaborators; and IRB/IEC members to inspect all facilities and records relevant to this study.

13.4. Drug Accountability

The investigator or designee (ie, unblinded pharmacist[s]) are responsible for ensuring adequate accountability of all used and unused study drug. This includes acknowledgment of receipt of each shipment of study drug (quantity and condition), subject drug dispensation records, and returned or destroyed study drug. Dispensation records will document quantities received from BeiGene's designated depot or its designee and quantities dispensed to subjects, including batch/lot number, date dispensed, subject identifier number, and the initials of the person dispensing the medication.

At study initiation, the monitor will evaluate the site's standard operating procedure for study drug disposal/destruction to ensure that it complies with BeiGene requirements specified in the Pharmacy Manual. At appropriate times during the conduct of the study or at the end of the study following final drug inventory reconciliation by the monitor, the study site will dispose of and/or destroy all unused study drug supplies, including empty containers, according to these procedures. If the site cannot meet BeiGene's requirements specified in the Pharmacy Manual for disposal, arrangements will be made between the site and BeiGene or its representative for destruction or return of unused study drug supplies.

All drug supplies and associated documentation will be periodically reviewed and verified by the study monitor over the course of the study.

